6.1.1 Screening/observation period (Day -42 to Day -1)

Patients (or their legally authorized representative) must provide informed consent before any study-specific screening tests are performed. Participating study sites are required to document all screened candidates initially considered for inclusion in the study. Patients will be designated as screened following completion of all screening assessments.

Screen failures are defined as patients who sign the informed consent form (ICF) but are not subsequently dosed with BIVV009. If a patient is considered a screen failure, the reason(s) will be documented on the screening log and in source records.

A minimal set of screen failure information is required to ensure transparent reporting of screen failure participants to meet the Consolidated Standards of Reporting Trials publishing requirements and to respond to queries from regulatory authorities. Minimal information includes demography, screen failure details, eligibility criteria, and any SAEs.

6.1.1.1 Screening assessments (initiating at Day -42)

The following assessments and procedures will be initiated following collection of written informed consent at Day -42 and completed during the 6-week Screening/Observation Period:

- Written informed consent
- Demographic data and baseline characteristics including height and body weight
- Detailed medical history
- Immunization review and vaccination, if applicable
- Serum pregnancy test (if applicable)
- Physical examination (full)
- Vital signs
- Virology/serology panel
- Gilbert's Syndrome testing (UGT1A1 gene)
- SLE panel
- Hematology panel
- Coagulation panel
- Clinical chemistry panel
- Urinalysis
- PD samples (refer to Laboratory Manual)
- Iron panel and erythropoietin assays
- Disease-related biomarkers
- 12-lead ECG
- Prior bone marrow biopsy report review, prior tissue assessment, or new bone marrow biopsy (as applicable)

- Optional bone marrow testing for MYD88 status
- Inclusion/exclusion criteria review for determination of eligibility
- Solicited symptomatic anemia assessment
- Record healthcare resource utilization data from previous 6 months
- Record prior and concomitant medications/procedures including transfusions
- Adverse event monitoring

The Screening/Observation Period may be extended by 1 week for patients requiring a blood transfusion during screening to ensure that first study drug administration occurs at least 1 week following the transfusion.

Bone marrow biopsy

A bone marrow biopsy is required to have been performed within 6 months of Screening to rule out overt evidence of lymphoproliferative disease or other hematological malignancy prior to enrollment. Sites will submit de-identified biopsy *reports* to an independent central reader for eligibility adjudication. If biopsy is deemed unsuitable or insufficient to determine eligibility, then either the prior tissue may be submitted for additional hematopathology assessment or a new bone marrow biopsy will be performed during the screening period. Patients will have the option to consent to additional testing of bone marrow for MYD88 status. Further instructions for bone marrow biopsy assessment will be available in the study procedural manual.

Vaccination against encapsulated bacterial pathogens

In the event a patient does not have documented vaccination against encapsulated bacterial pathogens (*Neisseria meningitidis*, including serogroup B *meningococcus* where available, *Haemophilus influenzae*, and *Streptococcus pneumoniae*) within 5 years prior to enrollment, vaccination should be initiated during the Screening/Observation Period prior to enrollment (see [Table 3](#)). Vaccination series for these pathogens should be completed as per current regional guidelines specified for patients with persistent complement deficiency and in accordance with their respective labels, as applicable. Where no regional guidelines are available for patients with persistent complement deficiency, it is recommended that vaccinations include meningococcal conjugate, meningococcal serogroup B, 13-valent pneumococcal, 23-valent pneumococcal, and *Haemophilus influenzae* type b vaccines where commercially available. Revaccination with booster doses should be given according to regional guidelines for patients with persistent complement deficiency and in accordance with respective labels.

Vaccinations should be initiated on Day -42 or as early as possible during the Screening/Observation period. The primary vaccine series should be completed during Screening when possible and otherwise prior to Week 5 of Part A. Patients must be advised that vaccination may not prevent meningococcal infections and that they should immediately report fevers or other symptoms consistent with acute infection to the Investigator.

Patients who develop symptoms consistent with an infection due to the encapsulated bacterial pathogens *Streptococcus pneumoniae*, *Neisseria meningitidis*, or *Haemophilus influenzae* during the study period will have a blood sample collected to test vaccine related titers if the infection is confirmed with one of the aforementioned organisms.

A separate vaccination schedule for Japan is provided in [Section 10.9](#), Appendix I.

Laboratory tests

The first set of laboratory test results collected during the Screening Period will be utilized to assess patient eligibility for the study. Screening assessments may be repeated once at the discretion of the Principal Investigator (PI). Additional repeat screening tests may not be performed without Sponsor (or designee) approval.

6.1.1.2 Interim visits during screening/observation period

During the 6-week Screening/Observation Period, the patient will return to the clinical site approximately every 2 weeks (Day -28 and Day -14) after the initial visit for collection of laboratory samples to assess and characterize their CAgD. During these visits the following assessments and procedures will be performed:

- Vital signs
- Collection of blood samples for assessment of the following indicators of CAgD:
 - Hemoglobin
 - Bilirubin
 - LDH
 - Haptoglobin
 - Reticulocytes
 - CH50
- Record prior and concomitant medications/procedures including transfusions
- Adverse event monitoring

Detailed information on sample collection and a list of analytes to be tested may be found in the Study Schedule of Events ([Table 3](#)) in [Section 6.1](#), [Section 10.1](#), Appendix A, and the Laboratory Manual.

6.1.1.3 Confirmatory review of patient eligibility

Upon completion of screening assessments, the site will compile de-identified, key eligibility data for each patient and forward to the Study Medical Monitor for review and confirmation of eligibility prior to study enrollment. Details on the eligibility data review forms and the adjudication process may be found in the study procedural manual.

6.1.2 Day 0 visit (first dose)

On Day 0, patients will undergo the following procedures before administration of the study drug:

- Inclusion/exclusion criteria for confirmation of continued eligibility
- Serum or urine pregnancy test (if applicable)
- Vaccine titers

- Body weight
- Physical examination (brief)
- Vital signs
- 12-lead ECG
- Hematology panel
- Coagulation panel
- Clinical chemistry panel
- Urinalysis
- Solicited symptomatic anemia assessment
- QOL assessments
 - FACIT-Fatigue (see [Section 10.3](#), Appendix C)
 - EQ-5D-5L (see [Section 10.4](#), Appendix D)
 - SF-12 (see [Section 10.5](#), Appendix E)
 - PGIC (see [Section 10.6](#), Appendix F)
 - PGIS (see [Section 10.8](#), Appendix H)
- ADAs against BIVV009
- PK and PD sampling
- Disease related biomarkers
- Record healthcare resource utilization data (see [Section 10.7](#), Appendix G) since previous assessment
- Record prior and concomitant medications/procedures including transfusions
- Adverse event monitoring

At 0 hour, study drug will be infused via an indwelling IV catheter over a period of 60 ±5 minutes. Patients with underlying cardiopulmonary disease may receive a 2-hour infusion with Sponsor approval. Additionally, study drug infusion may be interrupted or slowed in the event of suspicion of an allergic reaction or anaphylaxis.

After completion of the infusion, patients will undergo the following procedures:

- Vital signs at 1 hour (±5 minutes) postdose
- 12-lead ECG at 1 hour (±15 minutes) postdose
- PK and PD sampling at 1 hour (±15 minutes) postdose.

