6.1.5.3 Procedures to be performed every 3 months (unless noted otherwise)

In addition, the following procedures will be performed every 3 months beginning after Week 27 (or as otherwise noted) during Part B prior to administration of study drug:

- Body weight
- Physical examination (brief)
- Vital signs
- 12-lead ECG (once at 3 months [Day 273], and at end of treatment visit)
- Urinalysis
- QOL assessments:
 - FACIT-Fatigue
 - EQ-5D-5L
 - SF-12
 - PGIS
 - PGIC
- SLE panel (every 6 months)
- PK, PD and ADA sampling during the 1st year of treatment in Part B then every 6 months

At 0 hour, study drug will be infused via an indwelling IV catheter over a period of 60 ±5 minutes. Patients with underlying cardiopulmonary disease may receive a 2-hour infusion with Sponsor approval. Additionally, study drug infusion may be interrupted or slowed in the event of suspicion of an allergic or anaphylactic reaction.

After completion of the infusion, patients will undergo the following procedures:

- Vital signs at 1 hour (±5 minutes) postdose
- 12-lead ECG (once at 3 months [Day 273]) at 1 hour (±15 minutes) postdose, and at end of treatment visit
- PK and PD sampling (every 3 months during the 1st year of treatment in Part B then every 6 months) at 1 hour (±15 minutes) postdose.

PK, PD, and ADA samples will be collected if a patient experiences a hematologic breakthrough event (rapid fall in Hgb ≥ 2 g/dL associated with an increase in LDH/bilirubin and/or decrease in haptoglobin since the last scheduled visit).

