6.2.4 Dose preparation and administration

Qualified pharmacy or clinical staff will prepare each unit dose of study drug for IV infusion. Dose preparation shall proceed as detailed in the Pharmacy Manual for this study. Briefly, an appropriate number of 10 mL drug product vials (each containing 180 mg of BIVV009) or 25 mL drug product vials (each containing 1.1 grams of BIVV009) will be pooled and diluted with saline solution to a total volume of 500 mL to administer either a 6.5 gram dose (for patients <75 kg) or a 7.5 gram dose (for patients ≥75 kg), depending on the patient's baseline (Day 0) body weight. Details are provided in the Pharmacy Manual.

BIVV009 will be infused IV by a suitable infusion pump over a period of approximately 60 minutes. (Patients with underlying cardiopulmonary disease may receive a 2-hour infusion with Sponsor approval.) The infusion catheter and tubing will be flushed both immediately before and immediately following completion of the infusion with a sufficient quantity of sterile saline for injection. For each dose, the patient's actual dose and time of dosing and if the administration is being performed at the patient's home ([Section 10.10](#), Appendix J) will be recorded in the source documents and transcribed onto the eCRFs. The administration location, rate, start time, stop time, any infusion interruptions, and total volume of investigational product actually administered will be recorded in the eCRFs. If an AE occurs during the administration of study drug, the infusion may be slowed or stopped at the discretion of the Investigator or the professional healthcare caregiver in case of home infusions (see [Section 10.10](#), Appendix J).

Patients must be monitored for acute allergic reactions during infusion and for at least 2 hours after the completion of the first administration of study drug or 1 hour after the completion of each administration of study drug thereafter. Additionally, patients undergoing home infusions will be monitored by the professional healthcare caregiver for 2 hours after the completion of the first home infusion or 1 hour after the completion of each subsequent home infusion (see [Section 10.10](#), Appendix J). Like with office visits, medications such as epinephrine and diphenhydramine, and additional emergency equipment will be available in

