case an allergic reaction or anaphylaxis occurs during home infusion. Site personnel, or professional healthcare caregiver in case of home infusions (see [Section 10.10](#), Appendix J), must be qualified to detect and treat allergic reactions and anaphylaxis. See [Section 6.3.8](#) for further details regarding additional testing.

Patients should be instructed to report the development of rash, hives, pruritus, flushing, urticaria, etc, that may represent an allergic reaction to study drug. If any signs or symptoms of an allergic or anaphylactic reaction are observed during the infusion, administration of study drug must be immediately discontinued, and the patient treated as appropriate, and in case of home infusion, the investigator should be notified immediately (see [Section 10.10](#), Appendix J).

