6.3.8 Additional testing in case of hypersensitivity/allergic reaction

If a patient exhibits signs of a hypersensitivity/allergic reaction during study drug administration, the study drug infusion should be stopped immediately, and medical treatment provided, as appropriate.

If a suspected anaphylactic reaction occurs ([Simons 2010](#)), the following labs may be obtained per the discretion of the Investigator, after discussion with the Sponsor Medical Monitor:

- Approximately 30 to 120 minutes after the start of symptoms: blood draw for ADAs (including isotyping), tryptase, IL-6, IL-33, plasma histamine, CICs, and complement levels (CH50). A follow-up tryptase level should be obtained 8 days following the reaction.
- 24-hour urine collection for methylhistamine analysis (ideally collection should be started within 6 hours of onset of symptoms and collected even if the patient is sent to the emergency room; patient can be provided with a container for the collection).

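### The visit sections let staff slow the infusion on suspicion of an allergic reaction or anaphylaxis; Sections 6.2.4 and 6.3.8 tell them to stop it at once

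*Protocol*

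**What the plan says.** Five sections of the protocol bear on what staff do when an allergic reaction is suspected during an on-site infusion.

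- **Section 6.1.2 (Day 0):** "study drug infusion may be interrupted or slowed in the event of suspicion of an allergic reaction or anaphylaxis".
- **Section 6.1.3 (Weeks 1-25):** the same sentence, word for word.
- **Section 6.1.5.3 (Part B):** "study drug infusion may be interrupted or slowed in the event of suspicion of an allergic or anaphylactic reaction".
- **Section 6.2.4 (dose preparation and administration):** "If any signs or symptoms of an allergic or anaphylactic reaction are observed during the infusion, administration of study drug must be immediately discontinued". The sentence goes on to require treatment and, for home infusion, immediate notice to the investigator.
- **Section 6.3.8 (additional testing):** "If a patient exhibits signs of a hypersensitivity/allergic reaction during study drug administration, the study drug infusion should be stopped immediately".

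Section 6.2.4 also contains a general rule for adverse events, placed before the allergic-reaction rule: "If an AE occurs during the administration of study drug, the infusion may be slowed or stopped at the discretion of the Investigator". It extends the same discretion to the caregiver at home infusions.

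Appendix J (Section 10.10) repeats the mandatory stop rule in its own Section 6.2.4 text and does not offer slowing as an option.

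**The concern.** The visit sections and the two stop rules address the same event and prescribe different actions. Interrupting an infusion can be read as stopping it, although the visit sections make even that optional. Slowing cannot be read that way: the drug continues to enter the patient at a lower rate.

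This is a patient-safety matter. Staff working through a dosing visit may well use the visit section as their checklist. In all three visit sections that text names anaphylaxis or an anaphylactic reaction and still permits slowing. A member of staff who slows the infusion would be within the visit section while doing what Section 6.2.4 prohibits.

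There is a smaller consequence for trial conduct. A site that slowed an infusion could be judged compliant or in deviation, depending on which section the monitor applied.

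**Working it through.** No arithmetic decides this point, so the instructions are set side by side.

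| Protocol section | Trigger | Force | Action |
|---|---|---|---|
| 6.1.2, 6.1.3 | Suspicion of allergic reaction or anaphylaxis | Optional | Interrupt or slow |
| 6.1.5.3 | Suspicion of allergic or anaphylactic reaction | Optional | Interrupt or slow |
| 6.2.4, allergic-reaction rule | Any sign or symptom observed | Mandatory | Discontinue immediately |
| 6.3.8 | Signs exhibited by the patient | Directed | Stop immediately |
| 6.2.4, general rule | Any adverse event | Discretionary | Slow or stop |

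**Step 1: can the actions be reconciled?** Interrupting can, if it is read as stopping. Slowing cannot, because both stop rules require that the drug no longer runs.

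**Step 2: do the triggers separate the rules?** The visit sections speak of suspicion; Sections 6.2.4 and 6.3.8 speak of signs, or signs or symptoms. The protocol does not define the difference or give a grade at which slowing ends and stopping begins. During an infusion, suspicion arises from something staff see or the patient reports, and Section 6.2.4 applies to any such sign or symptom. The triggers therefore overlap in practice.

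**Step 3: does the general adverse-event rule reconcile them?** No. It covers adverse events as a whole, and the specific mandatory rule for allergic reactions comes after it in the same section.

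**Step 4: is the stop rule confined to home infusions?** No. Section 6.2.4 covers every infusion and only adds investigator notification for the home setting. Section 6.3.8 makes no reference to setting. Appendix J repeats the stop rule, which suggests that stopping is the intended standard.

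**Step 5: is there a precedence statement?** None was found. The infusion paragraphs in Sections 6.1.2, 6.1.3 and 6.1.5.3 do not refer the reader to Section 6.2.4 or 6.3.8.

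**Step 6: how many infusions are exposed?** Part A has 14 scheduled doses per patient (Part A SAP, Section 6.5.2). Protocol Section 4.4 gives 2 to 3 years of Part B dosing, every 2 weeks. At 52 weeks a year that is 2 × 52 / 2 = 52 to 3 × 52 / 2 = 78 infusions per patient. For patients on the home scheme, some of these are given at home. These figures count opportunities for the conflict to arise. They are not a risk estimate, because the documents give no rate of suspected reactions.

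**The case against.** The strongest case against the point has four parts.

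**Context.** In each visit section the sentence ends a paragraph about infusion duration: the 60 ±5 minute standard, then the 2-hour option for cardiopulmonary disease, then this permission. It can be read as leave to depart from the standard rate, with reaction management left to Section 6.2.4. That reading is fair to the likely intent. The sentence nevertheless names the reaction, states an action and contains no cross-reference, so a reader has no cue to look further.

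**Permission against obligation.** A permission does not ordinarily override a mandatory rule, and a site that always stops complies with every section. This is correct and limits the problem: no site is forced into a breach. The reader must, however, know the mandatory rule exists, and the visit section does not say so.

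**Graded triggers.** One could allow discretion on suspicion and require a stop once signs appear. The wording leaves room for this, but the protocol does not set it out, and Section 6.2.4 reaches any sign or symptom.

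**Safeguards.** Section 6.2.4 requires monitoring during every infusion, for at least 2 hours after the first dose and for 1 hour after later ones. It also requires personnel qualified to detect and treat anaphylaxis. Section 6.7.1.2 has Grade 3 or higher allergic reactions and anaphylaxis reported as serious. Many staff would stop whatever the visit section says, so the practical risk is lower than the text alone suggests. The safeguards do not remove the contradiction.

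A further objection, aimed at the remedy, has merit: requiring a stop on suspicion is slightly broader than requiring it on observed signs, and it could produce a few more partial doses.

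**Conclusion.** The concern holds. Three visit sections permit an action that Section 6.2.4 forbids and Section 6.3.8 advises against, for what is in practice the same event, and nothing in the protocol settles which applies. The text is wrong as written and should be corrected, because the event named includes anaphylaxis.

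The conclusion rests on two readings: that slowing means the drug continues to run, and that suspicion during an infusion rests on some observed or reported sign or symptom. The size cannot be quantified from the documents. The conflict is limited to on-site infusions, and monitoring and qualified staff reduce the chance of harm. It has no bearing on sample size, power, type I error or the primary responder analysis. It remains live under this amendment because Section 6.1.5.3 governs the extended Part B.

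**What to change.** In Sections 6.1.2, 6.1.3 and 6.1.5.3, replace the permission to interrupt or slow with an instruction that, on a suspected allergic or anaphylactic reaction, the infusion must be stopped immediately, with a reference to Sections 6.2.4 and 6.3.8. Keep slowing for non-allergic adverse events under the general rule in Section 6.2.4. Because that rule does not at present exclude allergic reactions, a short exception there would make the division explicit. Appendix J needs no change.

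The sponsor should also state whether an infusion stopped on suspicion may be restarted if a reaction is ruled out, since the present wording on interruption leaves that open.

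The cost is a wording amendment to three sentences, plus the short exception and the restart statement if adopted. No new data, visits or analyses are needed. Infusion interruptions and volume given are already recorded (Section 6.2.4), and the Part A SAP already summarizes partial infusions (Section 6.5.2), so any additional partial doses in Part A would be visible without new programming.

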6.1.3 Weeks 1-25

On Days 7, 21, 35, 49, 63, 77, 91, 105, 119, 133, 147, 161, and 175, patients will undergo the following procedures before administration of the study drug:

- Serum or urine pregnancy test, if applicable, on Days 21, 49, 77, 105, 133, and 161

- Physical examination (brief)
- Vital signs
- 12-lead ECG (Day 91 only)
- Hematology panel
- Clinical chemistry panel
- Solicited symptomatic anemia assessment
- QOL assessments
 - FACIT-Fatigue: all scheduled visits
 - PGIS: Days 35, 77, and 119 only
 - PGIC: Days 35, 77, and 119 only
 - SF-12: Days 35, 77, and 119 only
 - EQ-5D-5L: Days 49, 91, and 133 only
- PK and PD sampling
- ADA: In patients who consented to the use of their blood samples for future research, PD back-up samples collected at the following time points Day 7, 35, 77, 133 and 175, may be used to assay ADA.
- Disease-related biomarkers (subset at Day 91 only); refer to Laboratory Manual for details
- Record healthcare resource utilization data since previous assessment on Days 21, 49, 77, 105, 133, and 161
- Record concomitant medications/procedures including transfusions
- Adverse event monitoring

At 0 hour, study drug will be infused via an indwelling IV catheter over a period of 60 ±5 minutes. Patients with underlying cardiopulmonary disease may receive a 2-hour infusion with Sponsor approval. Additionally, study drug infusion may be interrupted or slowed in the event of suspicion of an allergic reaction or anaphylaxis.

After completion of the infusion, patients will undergo the following procedures:

- Vital signs at 1 hour (±5 minutes) postdose
- 12-lead ECG (Day 91 only) at 1 hour (±15 minutes) postdose
- PK and PD sampling at 1 hour (±15 minutes) postdose.

Vaccinations should be administered according to [Section 6.1.1.1](#), if applicable, or [Section 10.9](#), Appendix I for Japan.

Note: Patients who miss a dose (ie, outside the dosing window or >17 days since last dose) should return to the site for an unscheduled visit 1 week prior to the next scheduled dose in order to receive an additional loading dose. The patient should then resume subsequent dosing visits every 14 days after the loading dose.

